6.1 Patients randomised to receive NTB

All NTBs work on the same principles of action with no reason to suspect they differ in effectiveness. Individual centres will select which NTB they will use within the trial. The NTB must meet two key criteria: 1) CAD/CAM designed, as these braces are replacing older measurement and design techniques (37,38) and 2) logistically feasible to be used in the UK. Practically, orthotists will be given initial training in measurement, design, manufacture and fitting of the Providence brace, CMP brace (a CAD/CAM designed brace available in the UK) and training to help them produce their own CAD/CAM NTB if they have the equipment and skills locally to enable this. The Providence brace is the only brace manufactured outside the UK but does have a UK distributer.

The NTB will be prescribed for recumbent use at night-time only (8-12hrs each day) as recommended by the International Society on Scoliosis Orthopedic and Rehabilitation Treatment (SOSORT) Guidelines (39). A supine in-brace radiograph will be obtained to allow comparison with the standing radiograph. The correction of the curve supine, in brace measured as a percentage of the standing curve size is an important measure of brace quality and curve flexibility.

The Orthotist will be trained in the provision of their preferred NTB. There will be a training session or online training for NTBs with certification.

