6.2 Patients randomised to FTB

There are many different FTB designs being used in the UK. There is no evidence to show that one brace is better than another. There are 2 basic types of FTB: (1) Sym-

metrical thoracolumbosacral orthosis (TLSO) as used in the BrAIST study; (2) Asymmetrical braces which are designed using digital scanning and CAD/CAM +/- finite element modelling. Although asymmetrical braces compared with symmetrical FTBs produce better in-brace correction and are lighter but more expensive, there is no highquality evidence that they reduce the risk of curve progression to a surrogate marker of surgical treatment. The measurement and design of the FTB will be chosen by the Orthotist and spinal surgeon based on current practice, recording the method for measurement, the design process, and the brace type.

The FTB will be prescribed for 20-24 hours each day as recommended by the SO-SORT Guidelines (39). A standing in-brace radiograph will be obtained to allow comparison with the standing out-of-brace radiograph. The correction of the curve in brace measured as a percentage of the standing curve size is an important measure of brace quality and curve flexibility.

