6.3 Both braces

Sites should aim to have patients in brace within 8 weeks of consultant referral to reduce the risk of curve progression before bracing.

Following randomisation, the patient will attend a first clinic appointment with the Orthotist where they will be measured for their allocated brace. From these measurements, the brace will be designed and manufactured. The patient will return for a brace fitting appointment where the brace will be 'fine-tuned' (with pads if required). Once the brace is fitted, an in brace spinal radiograph either at the initial fitting or within the first 6 weeks in brace is obtained to ensure good curve correction. This will be done standing for the FTB and supine for the NTB. Further adjustments are permissible as required. The patient will be followed up as per local protocol, including regular brace check, adjustment, download of compliance data as required, and complications noted. A standing spine x-ray out of brace will be performed with an in-brace x-ray if required to guide brace adjustment. The patient will be reviewed by the spinal team to evaluate Cobb angle and skeletal maturity (Risser sign). All patients will have contact details for the spinal team, research team and orthotist for advice or concerns.

Braces will be renewed when required due to growth of the child. When a brace is renewed, the same protocol described above will be followed. Bracing will continue

until the patient reaches skeletal maturity (Risser 4 (girls) or Risser 5 (boys)), or until surgery is required. At this point, the brace can be discontinued.

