8.3 Internal pilot outcomes

Criteria are provided below to ensure feasibility of the RCT. Sheffield CTRU will aggregate study data to assess the feasibility of the research and intervention protocols based on the following feasibility outcomes: #At least one NTB/FTB designed, manufactured, fitted and provided to patient

Cross-over will not be assessed within the success criteria as too few patients will have reached the point at which cross-over would be considered (i.e. progression of their condition). Crossover will be monitored by the DMEC.

Domain	Target at end of internal pilot	Green	Amber	Red
Site set-up	19 centres set-up and re- cruited first participant	15 centres re- cruited first par- ticipant	12-14 cen- tres recruited first partici- pant	Fewer than 12 centres recruited first participant
Participant recruitment	Average of 1.1 participants recruited per centre, per month	Minimum 80% of target (per centre per month)	70-79% of target (per centre, per month)	Below 70% of target (per centre, per month)
Retention & cobb angle collection (primary outcome)	gle collection points those randomised col-		70-89% of target	Below 70% of target
Intervention deliv- ery	100% of participants receive the treatment they are ran- domised to [#]	100% of target	85-99% of target	Below 85% of target
Minimum wear time in NTB arm	Participants randomised to do so wear the NTB brace for the prescribed wear time (8-10 hours/day)	Median wear time of at least 7 hours/day	Median wear time of 5-7 hours/day	Median wear time of less than 5 hours/day
Minimum wear time in FTB armParticipants randomised to do so wear the FTB brace for the prescribed wear time (20-23 hours/day)		Median wear time of at least 12 hours/day	Median wear time of 10-12 hours/day	Median wear time of less than 10 hours/day
Compliance data	Compliance data available for 100% of participants who have received a brace and have attended at least one follow-up appointment	Minimum 80% of target	70-79% of target	Below 70% of target

9. Assessments and procedures

All clinical data will be entered by the research site staff onto the British Spine Registry (BSR); PROMs data will also be entered directly onto this system by the patient, with paper copies available if this is not possible. The BSR is an existing national register

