9.2 Patient Timeline from Eligibility to first 6 month appointment

• Day 0: Screening visit: Seen in clinic and X-rayed to determine eligibility and given information

BASIS Study

- Week 0-7: Telephone call from Research Team+ e-consent + randomisation (may be in person if patient prefers at clinic visit). This may be delayed if the patient is sent for a spinal MRI
- Week 2-6: Brace measurement (after randomisation)
- Week 4-8: Brace fitting
- In brace XR within 6 weeks of brace fitting
- Week 26: First follow-up 6 months after randomisation.

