11.2 Statistical Analysis

The trial will be analysed and reported according to CONSORT guidelines for noninferiority designs (54).

The ITT population (and safety) populations will consist of all participants who consent and are randomised to receive FTB or NTB.

The per protocol (PP) will be defined for participants in the FTB group, as

receiving the FTB treatment as documented in the study protocol (see Section 6)
 Complying and adhering to the treatment they were assigned to. Compliance with FTB would mean wearing the brace for average of >12.9hrs/day (= >65% of the minimum prescribed time) over the post-randomisation follow-up period.

For the NTB group, the PP population will be defined as

1) receiving the NTB treatment as documented in the study protocol

2) Complying and adhering to the treatment they were assigned to. Compliance with NTB would mean wearing the brace for average of >5.2hrs/day (= >65% of the minimum prescribed time) over the post-randomisation follow-up period.

Patients who cross-over from NTB to FTB will be removed from the PP population for the analysis of the primary outcome.

The binary primary outcome is curve progression to 50 degrees or more (treatment failure) before skeletal maturity and skeletal maturity without this degree of curve progression (treatment success). Non-inferiority for the primary outcome will be declared if the two-sided 95% confidence interval (equivalent to a one-sided 97.5%) for the risk difference in the event rate of progression to 50 degrees between the NTB group and the FTB group does not exceed 11%. The analysis will be completed using a Generalized Linear Model (GLM) with binomially distributed response and identity link (55) adjusted for baseline covariates (site, skeletal maturity Risser score 0, 1 or 2, and Cobb angle). This will be conducted on both an intention-to-treat (ITT) population and per protocol (PP) basis. The adjusted differences in failure rates, along with 95% con-fidence intervals will be calculated and presented.

Missing data

For the primary outcome, curve progression to 50 degrees or more (treatment failure) and skeletal maturity without this degree of curve progression (treatment success) any missing outcome data will be imputed through a default "worst" case scenario (i.e. assume treatment failure) and "best" case scenario (i.e. assume treatment success) and the results compared with the available data analysis.

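### The full-time brace (FTB) per-protocol cut-off does not equal its stated percentage (12.9 h is 64.5% of 20 h; 65% is 13.0 h), and its averaging window does not match the period of brace wear

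*Protocol*

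**What the plan says.** Section 11.2 defines the per-protocol (PP) population partly by wear time. For FTB, compliance means "wearing the brace for average of >12.9hrs/day (= >65% of the minimum prescribed time) over the post-randomisation follow-up period". For NTB it means "wearing the brace for average of >5.2hrs/day (= >65% of the minimum prescribed time) over the post-randomisation follow-up period". The risk difference is compared with the 11% margin in both the intention-to-treat and the PP population.

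The minimum prescriptions are set elsewhere. Section 6.2 states: "The FTB will be prescribed for 20-24 hours each day". Section 6.1 gives 8 to 12 h for NTB. The pilot table in 8.3 gives "20-23 hours/day" for FTB and 8 to 10 h for NTB. The upper ends differ between sections, but the cut-offs rest only on the lower ends, which agree at 20 h and 8 h.

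On timing, section 9.2 places the brace after randomisation ("Week 4-8: Brace fitting", counted from screening). Section 6.3 (Both braces) continues bracing to skeletal maturity or surgery and then says: "At this point, the brace can be discontinued". Section 9 continues follow-up after 50 degrees, after surgery, and at 12 and 24 months after maturity.

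**The concern.** There are two separate faults in one definition.

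First, the FTB number and its percentage cannot both be applied. A patient averaging 12.95 h/day passes on the number and fails on the percentage. The NTB arm has no such conflict.

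Second, the period over which wear is averaged is not the period in which wear is prescribed and recorded. It includes days before a brace exists. Taken at its word, it also includes days after bracing has properly ended. Counting such days as zero lowers the average by an amount that depends on how long the patient was followed and when the endpoint came, not on adherence.

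The PP set feeds the non-inferiority comparison. A membership rule that can depend on outcome is undesirable there, because it could remove treatment failures selectively.

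**Working it through.** **Cut-offs.** The formula is 0.65 × minimum prescribed hours.

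- NTB: 0.65 × 8 = 5.2 h. The plan's figure is reproduced.
- FTB: 0.65 × 20 = 13.0 h. The plan's 12.9 h is not reproduced.
- In reverse, 12.9 / 20 = 64.5%, and 12.9 h would be 65% of 12.9 / 0.65 = 19.85 h, a minimum that appears nowhere in the protocol.

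The discrepancy is 13.0 − 12.9 = 0.1 h, or 6 minutes a day. It lies close to where FTB wear is expected: section 2.1 cites a mean of 12.1 h/day in the earlier bracing trial, and 8.3 sets the pilot's green level at a median of at least 12 h/day. The protocol gives no spread of wear, so the number of patients between 12.9 and 13.0 h cannot be calculated.

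**Averaging window, stopped at maturity.** Let h be the hours worn on each braced day, T the months from randomisation to maturity, and g the months from randomisation to fitting. With unbraced days counted as zero, the average is h × (T − g) / T.

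Inputs: T = 28 months (Trial Summary, 28 +/- 9). The gap g is assumed to be 4 to 8 weeks, or 0.92 to 1.84 months. Section 9.2 counts weeks from screening, so the true gap can be shorter, and the effect then shrinks.

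- At h = 20: 20 × 27.08 / 28 = 19.3 h, and 20 × 26.16 / 28 = 18.7 h. Both pass easily.
- Such a patient fails only if T is below 20g / (20 − 12.9), which is 2.6 to 5.2 months.
- In-brace wear needed to average 12.9 h: 12.9 × 28 / 27.08 = 13.3 h, and 12.9 × 28 / 26.16 = 13.8 h. That is 66.7% to 69.0% of 20 h.
- For NTB, to average 5.2 h: 5.2 × 28 / 27.08 = 5.4 h, and 5.2 × 28 / 26.16 = 5.6 h.
- The requirement varies with T. For FTB it is 13.6 to 14.3 h at T = 19 and 13.2 to 13.6 h at T = 37.

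So under this assumption the fitting gap shifts the effective FTB cut-off by 0.4 to 0.9 h at 28 months, which is more than the arithmetic slip. The shift concerns patients near the threshold.

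**Averaging window, run past the endpoint.** Take a patient wearing the FTB 20 h/day who reaches 50 degrees at month 12, is assumed to stop bracing then, and is followed to month 28.

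- Averaged to month 28: 20 × (12 − 0.92) / 28 = 7.9 h, and 20 × (12 − 1.84) / 28 = 7.3 h. Fails.
- Averaged to month 12: 20 × 11.08 / 12 = 18.5 h, and 20 × 10.16 / 12 = 16.9 h. Passes.

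Adherence is the same in both cases. Only the end of the window changes the classification.

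**The case against.** The arithmetic slip is half a percentage point, and 64.5% rounded half-up is 65%. Thus 12.9 h may be the intended figure and 65% its rounded description. This stands: the documents do not show which was meant. They do show that the two disagree as written and that only the FTB arm is affected.

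A reader might go further and infer that the PP set would be nearly empty, or that fully compliant patients would ordinarily fail. With 24 months after maturity added as zeros, a patient at 20 h/day averages 20 × 27.08 / 52 = 10.4 h, or 20 × 26.16 / 52 = 10.1 h, below 12.9. An NTB patient at 8 h/day averages 4.2 to 4.0 h, below 5.2. The documents do not support that inference. Section 6.3 (Compliance monitoring) has the sensor cover the duration of bracing, 8.2 limits compliance collection to that time, and the schedule in 9.1 shows sensor data only up to maturity. Section 11.2 does not say to fill later months with zeros. On the more natural reading, to maturity, the same patient averages about 19 h and passes.

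It can also be said that exact start and stop rules belong in the analysis plan, which 11.2 promises for detailed methods. That has force for fine detail. But 11.2 defers the definition of non-adherence only for the time-to-event PP analysis. For the binary primary outcome it fixes the thresholds and names the window itself, so the text it fixes should be right.

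**Conclusion.** Both parts hold, in limited form.

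The mismatch between 12.9 h and 65% is certain and small. It affects only FTB patients averaging between 12.9 and 13.0 h/day, and it leaves the arms at 64.5% and 65% under a rule presented as common to both.

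The window does not match the period of prescribed and recorded wear. Its effect depends on the reading. If it ends at maturity, it tightens the FTB threshold by about 0.4 to 0.9 h/day at 28 months, assuming a 4 to 8 week gap and zero wear before fitting. A fully compliant patient still passes except at very short times to maturity. If it runs past 50 degrees, surgery or maturity, PP membership could depend on outcome and length of follow-up. Other sections suggest that braced time was intended, so this is an ambiguity to close, not evidence that the PP analysis would collapse.

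The correction should be made, because the definition decides who enters a population used for the 11% comparison. Nothing here bears on which wear time is clinically right.

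**What to change.** In section 11.2:

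1. Reconcile the FTB figure and percentage, so that both arms use the same stated proportion of the minimum prescriptions in 6.1 and 6.2. If 65% is kept, the FTB analysis cut-off is 13.0 h. If 12.9 h was intended, the percentage and the NTB figure need to be brought into line with it.
2. State that wear for this analysis is averaged from brace fitting to the earliest of 50 degrees, surgery, skeletal maturity or end of follow-up.
3. State how time counts after a patient stops the brace early. Section 9 keeps such patients in follow-up, and averaging over braced time alone would ignore the months after they stopped. Counting those months as zero wear is one option.

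The cost is a short text change, repeated in the analysis plan and made before the statisticians are unblinded. It needs no extra data and changes no prescribed wear.

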6.4 Cross-over

Some scoliosis curves will progress despite brace treatment. The spinal team and orthotist in each centre will be aware that this is monitored by the DMEC for each brace type. Cross-over from NTB to FTB will be discouraged and monitored.

The risk of curve progression reduces after peak height velocity (40) and most patients will be beyond this before progression is noted. Instead, high compliance with the NTB will be encouraged.

Switching will not be permitted from FTB to NTB as this treatment is not currently available on the NHS. If patients wish to switch from NTB to FTB, they will be asked for their reasons why.

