of spinal patients currently used to evaluate surgical patients and is familiar to the clinical staff in each centre, and an efficient means of follow-up in routine use. The central team will ensure data quality and data completeness is optimised.

Data Management (CRF design, data cleaning and validation) will be provided by the CTRU. Project-specific procedures for data management will be detailed in a data management plan.

Data will be collected in three phases:

Phase 1: Pre-skeletal maturity

Whilst in brace, patients will be seen routinely every 6-months for clinical monitoring, anchored from the date of randomisation. Routinely collected out-of-brace spinal radiographs will be taken at each visit in order to measure the Cobb angle (primary outcome). This is accepted as best practice guidelines for bracing in AIS (49). Such radiographs will be sent through the Image Exchange Portal and clinical data entered onto the BSR by research staff. Before the 6 month visit, parents and/or patients will be emailed a link to the questionnaires in the BSR which would be labelled for either 'patient' or 'parent' completion. If not completed, they will use a computer or tablet in the clinic to complete the questionnaires, with paper forms available as a back-up. Questionnaire completion will be checked and chased by mail or telephone as required.

There are a few scenarios:

- If the primary outcome is reached (progression to 50 degrees) before skeletal maturity, follow up will continue via email link to the BSR which will collect PROMs every 6 months
- If the patient has surgery, radiographs and questionnaires will be collected at routine post-operative clinic follow-up at 6-8 weeks, 1 year and 2 years after surgery.
- If the patient changes from NTB to FTB (cross-over), the reason will be recorded. Cross-over in the other direction is not allowed. Follow-up will continue unchanged.
- If the patient stops bracing altogether, follow-up will be continued.
- Rarely, during follow-up, patients will develop symptoms that prompt a spinal MRI scan. If this shows spinal dysraphism (dilated central canal is not defined as spinal dysraphism) as the cause for their scoliosis, the patient will continue in the trial for analysis on 'intention to treat' (ITT) but will be excluded from the per protocol (PP) analysis.

Phase 2: Post-skeletal maturity

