11.1 Sample size

In the BrAIST trial 28% of braced patients progressed to 50 degrees or more before skeletal maturity, which was the primary endpoint (5), so assuming this for the FTB group, with a non-inferiority margin of 11%, 90% power, 2.5% one-sided significance level and 10% attrition, the study will require 780 participants (390 per group).

This margin was chosen based on participants and parents. They have stated there is considerable functional and psychological benefit from not wearing braces during the daytime. During both PPI focus groups patients have expressed mixed views about FTB, which some were being treated with, and the concept of NTB. Approximately 50% of the group expressed a preference for a NTB. In our SAUK survey, 60% said

they would prefer a NTB compared to 27% for a FTB (and 7% no brace, 6% no answer).

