Time to event analysis will also be completed on the primary outcome data. This will also be considered on an ITT and PP basis. For the PP analysis non-adherers will be censored at the time at which they begin to non-adhere - what is defined as non-adherence will be pre-specified after discussion with clinical experts, including the DMEC and TSC. To account for potential time dependent confounding an inverse probability weighting (IPW) approach will be used to estimate the PP treatment effect (56). This is important because non-adherence might be related to prognosis, and therefore censoring non-adherers may represent informative censoring and induce selection bias. In addition, an analysis that adjusts specifically for any treatment crossover that occurs will be undertaken. The IPW approach will again be used for this analysis, as will a rank preserving structural failure time model (RPSFTM), in line with recommendations made by the National Institute for Health and Care Excellence (NICE) Decision Support Unit for adjusting (when relevant) for treatment switching in randomised controlled trials (57).

For the secondary outcome of Cobb angle, a longitudinal analysis of all time points will be used to assess the difference on a non-inferiority basis between the two groups. This analysis will use a linear mixed-model including the all available time points, other important potential baseline confounders (such as Risser score 0, 1 or 2, and baseline Cobb angle) and site as a random effect.

Patient reported repeated outcome measures will be assessed over time using summary measures such as Area Under the Curve on a superiority basis (58).

Data on adverse events and serious adverse events will be tabulated at the end of the trial and presented by treatment arm. This will include the number and percentage of participants reported as having any adverse event.

Detailed statistical methods for all outcomes and scenarios will be described in a related trial Statistical Analysis Plan written before the data is analysed according to the Sheffield CTRU standard operating procedures approved by the TSC and DMEC (both of which have independent statistical members).

Economic evaluation

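### The binary per-protocol analysis drops NTB patients who switch to FTB, a one-arm exclusion tied to progression, and the planned weighting is not carried to the 11% comparison

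*Protocol*

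**What the plan says.** Protocol section 11.2 judges the primary outcome, progression to 50 degrees before skeletal maturity, by the 95% confidence interval for the NTB minus FTB risk difference against 11%. A binomial identity-link model is fitted on both the ITT and the PP sets. On cross-over it says: "Patients who cross-over from NTB to FTB will be removed from the PP population for the analysis of the primary outcome".

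Three other places bear on that rule.

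- Section 6.4: "Switching will not be permitted from FTB to NTB as this treatment is not currently available on the NHS". The phase 1 scenarios in section 9 repeat this: "Cross-over in the other direction is not allowed. Follow-up will continue unchanged".
- Section 8.3 leaves cross-over out of the pilot criteria because too few patients will have reached "the point at which cross-over would be considered (i.e. progression of their condition").
- Section 11.2, on the PP time-to-event analysis, warns that "censoring non-adherers may represent informative censoring and induce selection bias". It plans IPW there, and IPW plus a rank preserving structural failure time model (RPSFTM) for a separate cross-over analysis. No such correction is stated for the binary PP model.

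The PP definition also sets wear-time limits: an average above 12.9 hours a day for FTB and above 5.2 hours a day for NTB.

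**The concern.** The rule can remove patients from the experimental arm only. A progressing FTB patient has no matching exit. Because the named trigger is progression and the endpoint is progression to 50 degrees, the rule selects on a post-randomisation event that is likely to predict failure. If switchers fail more often than the NTB patients who remain, the PP failure rate in NTB falls and the comparison leans towards non-inferiority.

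In a non-inferiority trial the PP analysis is usually read as a check on the ITT result. A PP set from which likely NTB failures have been removed is a weaker check. The exclusion is also not forced by missing data, since switchers stay in follow-up and their outcomes should be known. The protocol sees the problem for the time-to-event analysis, but not for the comparison that is tested against the margin.

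**Working it through.** **Inputs from the protocol.** Section 11.1: "In the BrAIST trial 28% of braced patients progressed to 50 degrees or more before skeletal maturity", and "with a non-inferiority margin of 11%, 90% power, 2.5% one-sided significance level and 10% attrition", giving 780 participants (390 per group).

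**Inputs assumed.** The protocol gives neither the share of NTB patients who switch (c) nor their failure risk (q). Both are varied below.

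**Reproducing the sample size.** n per arm = (1.960 + 1.282)² × 2 × 0.28 × 0.72 / 0.11² = 350.1, so 351. With 10% attrition, 351 / 0.90 = 390 per arm, 780 in all. This matches the protocol.

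**Effect of the rule on its own.** Put NTB exactly at the margin: true risks 28% (FTB) and 28% + 11% = 39% (NTB), with 351 evaluable per arm. After switchers are removed:

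- NTB risk in the PP set: p = (0.39 − c × q) / (1 − c)
- PP risk difference: RD = p − 0.28
- SE = √[p(1 − p) / (351(1 − c)) + 0.28 × 0.72 / 351]
- Chance of declaring non-inferiority = Φ((0.11 − RD) / SE − 1.96)

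Worked case, c = 10% and q = 60%: p = (0.39 − 0.06) / 0.90 = 0.3667; RD = 8.7 points; SE = 0.0362; Φ((0.11 − 0.0867) / 0.0362 − 1.96) = 9.4%. A simulation of 200,000 trials also gave 9.4%.

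| Switch (c) | Switchers who fail (q) | PP difference | False non-inferiority, PP alone |
|---|---|---|---|
| none removed | – | 11.0 points | 2.5% |
| 2% | 60% | 10.6 points | 3.3% |
| 5% | 60% | 9.9 points | 4.9% |
| 10% | 50% | 9.8 points | 5.2% |
| 10% | 60% | 8.7 points | 9.4% |
| 10% | 70% | 7.6 points | 16% |
| 10% | 28% | 12.2 points | 1.1% |

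The last row is the reverse case, in which switchers fail less often than the other NTB patients. At q = 39%, the arm average, there is no shift.

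**Adding the FTB wear-time exclusion.** Keep c = 10% and q = 60%, and also drop low-wear FTB patients (share and risk again assumed).

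- 20% of FTB dropped at 40% risk: FTB risk = (0.28 − 0.08) / 0.80 = 25.0%; net difference 36.7 − 25.0 = 11.7 points; false non-inferiority 1.6%.
- 30% dropped at 32% risk: FTB risk = (0.28 − 0.096) / 0.70 = 26.3%; net difference 10.4 points; 3.6%.

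The sign of the net bias therefore depends on quantities that the protocol does not give.

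**ITT in the same simulation** (c = 10%, q = 60%): ITT alone declared non-inferiority in 2.5% of trials, and ITT and PP jointly in 2.5%.

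**The case against.** Four arguments have weight.

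1. *The cross-over rule is only one of several PP exclusions.* This stands. Section 2.1 cites mean FTB wear of 12.1 hours a day in the earlier bracing trial (on an 18-hour prescription), below the 12.9-hour limit here, and mean night-brace wear of 7.2 hours, above the 5.2-hour limit. The wear rule may therefore remove more FTB than NTB patients. If low-wear FTB patients fail more often, that pushes against non-inferiority. A reader might infer that the PP analysis as a whole is biased towards non-inferiority; the protocol does not establish that. An offset that nobody planned is still no safeguard.

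2. *ITT is also run and keeps switchers.* This stands too. A reader might infer that ITT errs in the same direction because FTB rescues some NTB failures. That holds only if the target is the effect of NTB without switching. For the policy of starting on NTB, which is the question section 11.2 poses for the economic evaluation, ITT keeps its 2.5%. The rates in the table are for PP alone, not for the trial's conclusion.

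3. *Switching may be rare or have other causes.* Section 6.4 discourages cross-over, and patients may ask to switch for their own reasons, which are recorded. At 2% switching the effect is small, and it can reverse. Progression is nevertheless the only trigger the protocol names.

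4. *The correction is already planned.* In part. IPW and RPSFTM are described for the time-to-event analysis. A statistical analysis plan, not seen here, may extend them, but plain exclusion for the primary outcome is written into the protocol.

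**Conclusion.** The point holds for this rule taken alone. The exclusion acts on NTB only, is tied by the protocol to progression, and is left unweighted in the comparison judged against 11%. Its direction is towards non-inferiority provided that switchers fail more often than other NTB patients.

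Its size is unknown. For a true difference at the margin, false non-inferiority in the PP analysis alone runs from 3.3% (2% switching, 60% failing) to 16% (10%, 70%), and falls to 1.1% if switchers do better than the rest (10%, 28%). All of these rest on assumed switching shares and risks.

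Neither the net bias of the full PP set nor an inflated error for the trial as a whole is shown. This is a should-fix point.

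**What to change.** For the binary primary outcome, replace plain exclusion as the main PP analysis with the weighting already planned in section 11.2. Censor at the switch or at the start of non-adherence in both arms, apply the weights, estimate the risk of reaching 50 degrees by skeletal maturity in each arm, and compare the difference with 11%. Deleting the cross-over sentence would not be enough, because the PP definition would still require adherence to the assigned brace.

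Keep plain exclusion as a labelled sensitivity analysis. Add two more: one that retains switchers with their observed outcome, and one that counts a switch after documented progression as an NTB failure. The second is deliberately severe: at 10% switching and 60% risk it gave 0.1% false non-inferiority in the simulation.

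Cost: protocol and analysis-plan wording, some programming, and a slightly wider PP interval. The follow-up of switchers is already planned. The change should be made before the statisticians are unblinded, so that it cannot look driven by the data.
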